5.2. Participant Accountability

Disposition will be summarized for all subjects enrolled by safety analysis groups (see Appendix 9). The summary data will include number of subjects enrolled, number of subjects withdrawn prior to dosing, number (%) of subjects dosed, number (%) of subjects who completed the treatment/study, and number (%) of subjects who discontinued treatment and/or withdrew from the study. The denominator for all the percentage calculation is the number of subjects dosed. For subjects who discontinued treatment and/or withdrew from the study, the reasons for discontinuation and/or withdrawal, days on treatment and days on study will be listed. The disposition will also be summarized by core period and LTE period separately.

Number of subjects dosed will be summarized by feeder studies.

5.3. Demographic and Baseline Characteristics

Demographics, baseline characteristics, medical history and AD treatment history will be summarized for the mITT population.

The demographic data including age, gender, ethnicity, race, height, weight, and body mass index (BMI) will be summarized. Age will also be categorized and presented using the following subgroups: <=60, 61-70, 71-80, 81-85, >85. In addition, Asian ethnicity will be summarized for the following subclassification: Chinese, Indian, Japanese, Korean, and other.

Summary of the baseline characteristics of AD includes

, 221AD304 baseline clinical assessment including CDR global score, CDR-SB,
CDR cognitive subscore, CDR functional subscore, MMSE, ADAS-Cog 13,
number of years of formal education, number of years since first AD symptom, number of years since diagnosis of AD, and AD symptomatic medication use at 221AD304 baseline (yes or no; see Section 5.5.2 for definition of AD symptomatic medication use at 221AD304 baseline).

MMSE will also be categorized by the following subgroups: \leq 10, 11-20, 21-26, 27-30. Subject listings will be generated for demographics and baseline characteristics.

Medical history collected at EMBARK baseline will be coded using the Medical Dictionary for Regulatory Activities (MedDRA version 26.1 or later). The number (%) of subjects with history

Study: 221AD304 Version: 2.0

(including both ongoing and not ongoing medical conditions) will be summarized by system organ class and preferred term.

5.4. Protocol Deviations

Protocol deviations identified during site monitoring will be captured in a Protocol Deviation log and categorized as major or minor deviations based on Protocol Deviation Classification. The major protocol deviations will be summarized for the mITT population. Major and minor protocol deviations for all mITT subjects will be listed. Major protocol deviations related to COVID-19 will be summarized and all protocol deviations related to COVID-19 will be listed.

Subjects with protocol alternations due to COVID-19 will be listed based on the data on the protocol alternations due to COVID-19 collected from the COVID-19 Impact log CRF page.

5.5. Study Treatment Exposure and Concomitant Medications

5.5.1. Study Treatment Exposure and Study Drug Compliance

Summary of study drug exposure and compliance will be provided. Number of infusions (aducanumab) received will be summarized as a categorical variable (categories of 1-5, 6-10, 11-15, 16-20, 21-25, 26-30, 31-35, 36-39, and >39) as well as a continuous variable. Number of weeks on study treatment (aducanumab), calculated as (date of last dose – date of first dose +29)/7, will be summarized as a categorical variable (every 8 weeks) as well as a continuous variable. Percentage of study treatment taken up to the last dose, calculated as (the actual number of infusions / by the number of infusions a subject is expected to take until the date of last infusion) ×100, will be summarized as a continuous variable.

Due to the use of titration regimen in the study and possible dose suspension due to ARIA, another summary table will be provided including the following information in the study: number of infusions at each dose level (1 mg/kg, 3 mg/kg, 6 mg/kg and 10 mg/kg, respectively) summarized as a categorical variable as well as a continuous variable, number of subjects with dose increase (1 to 3 mg/kg, 3 to 6 mg/kg and 6 to 10 mg/kg, respectively), maximum dose level received, and cumulative dose (as a continuous variable).

Both drug exposure/compliance and titration summary tables will be repeated for the core period.

A listing of study drug administration records, including dose level at each infusion, cumulative number of infusions and cumulative dose will be provided.

5.5.2. Concomitant Medications and Non-Drug Therapies

The number (%) of subjects taking concomitant medication and non-drug therapies will be summarized for the mITT population. Concomitant medications and non-drug therapies will be listed.

All concomitant medications will be coded using the World Health Organization (WHO) medication dictionary. All concomitant non-drug therapies will be coded using the MedDRA dictionary (version 26.1 or later). A concomitant medication/therapy will be defined as any therapy that was taken on or after the day of the first dose of study drug. This includes therapies

Study: 221AD304 **Version:** 2.0

that start prior to the initiation of the first dose if their use continues on or after the date of first dose. To define concomitant use for therapies with missing start or stop dates, the following additional criteria will be used:

- if both the start and stop dates of a therapy are missing, that therapy will be considered concomitant.
- if the start date of a therapy is missing and the stop date of that therapy fall on or after the date of the first dose, that therapy will be considered concomitant.
- if the start date of a therapy is prior to the date of the first dose and the stop date of that therapy is missing and the therapy is listed as continuing, that therapy will be considered concomitant, or
- if the start date of a therapy is prior to the date of the first dose and the stop date of that therapy is missing and the therapy is not listed as continuing, that therapy will be considered non-concomitant.

For a therapy with a partial start date, the year/month of the therapy date will be compared to that of the first dosing date to determine whether the therapy is concomitant.

AD symptomatic medications taken concomitantly at 221AD304 baseline are defined as AD symptomatic medications that were being taken at the time of the first dose in 221AD304 study, i.e., started prior to the first dose and continued until after the first dose. AD symptomatic medications are defined as anticholinesterase (cholinesterase inhibitors) and memantine drugs in the WHO medication dictionary (version: WHODrug Global B3 Sep2023 or later version if applicable).

The number (%) of subjects taking concomitant AD symptomatic medications, number of subjects using Cholinesterase inhibitors only, Memantine only, or both at the 221AD304 baseline will be summarized.

5.6. Efficacy Endpoints

As discussed in Section 2.1, no efficacy analysis will be performed.

5.7. Safety Endpoints

5.7.1. General Considerations

The primary estimand employs the treatment-policy strategy to evaluate the safety of BIIB037 determined by the following 4 attributes:

- Population: Intended population for BIIB037 defined through the study inclusion/exclusion criteria. All subjects in the safety population will be used in analyzing this estimand
- Variable: adverse events

Product: Aducanumab
Study: 221AD304
Statistical Analysis Plan
Version: 2.0

• Handling intercurrent events: regardless of intercurrent events including treatment discontinuation and use of concomitant therapies

• Population-level summary: incidence of adverse events

The Safety population will be used for safety analyses of AEs, clinical laboratory data, Columbia Suicide Severity Rating Scale (C-SSRS) data, ECG data and vital sign data (all the safety data except for ARIA data). Safety MRI population will be used for analyses of ARIA data.

In general, AEs will be summarized based on incidence and incidence proportion. Incidence is defined as the number of subjects who experienced an event. Incidence proportion (%) is defined as the number of subjects who experienced an event divided by the total number of subjects in the analysis population, i.e., percentage. Each subject will be counted only once within each category.

All AEs will be coded using the MedDRA dictionary (version 26.1).

When analyzing data for the core period or LTE period, an event will be assigned to one period by the start date. The event duration will be based on the start date and the end date of that event.

5.7.2. Clinical Adverse Events

5.7.2.1. Treatment-emergent AEs (TEAEs)

All AEs will be analyzed based on the principle of treatment emergence. A treatment-emergent AE is defined as an AE that started or worsened after the start of first infusion of study treatment in 221AD304 study.

To define treatment emergence for AEs with missing start or stop date or time the following additional criteria will be used:

- if both the start and stop dates for a particular AE are missing, then that AE is considered treatment emergent;
- if the start date for a particular AE is missing and the stop date/time falls after the first dose date/time, then that AE is considered treatment emergent;
- if the start date for a particular AE was the same as the first dose date, and the start time was missing, then that event is considered treatment emergent.

For AEs with a partial start date, the year/month of the event date will be compared to that of the first dosing date to determine whether the event is treatment emergent.

Only TEAEs will be included in the AE tables, unless otherwise specified. Listings of AEs will include all events, whether treatment-emergent or not.

5.7.2.2. Summary and incidence analysis

An overall summary of AE table will be presented by safety analysis group as well as safety analysis group stratified by

The following information will be summarized: the number of subjects with any AE, with any AE by maximum severity, the

Study: 221AD304 Version: 2.0

number of subjects with any related AE (related to study drug as assessed by investigator), the number of subjects with SAEs, the number of subjects with related SAEs, the number of subjects with AE leading to study drug discontinuation, the number of subjects with AE leading to study withdrawal, and the number of subjects with a fatal event.

Table 4 lists the planned analyses of all AEs, most frequently reported AEs, related AEs (related to study drug as assessed by the investigator), AEs by severity, serious AEs, AE led to drug interrupted or drug withdraw, AE led to discontinuation of treatment, AE led to withdraw from study, and fatal events. All analyses will present incidence proportion by safety analysis groups for the overall study. Where indicated, the analyses will be repeated by safety analysis groups stratified by

The sorting order of AE incidence tables, unless otherwise specified, will be by decreasing frequency order of "BIIB037 total" column within each category in the tables presented by safety analysis group, and by decreasing frequency order of last column within each category in the tables presented by safety analysis group stratified by laboratory. A subject is counted only once within each category in each table. For example, for the table of AEs by system organ class and preferred terms sorted by decreasing frequency presented by safety analysis group, system organ class will be presented in decreasing frequency order of BIIB037 total column, and within each system organ class, preferred terms will be presented in decreasing frequency order of BIIB037 total column. A subject is counted only once within each system organ class and preferred term.

Table 4 List of Planned Analyses for AE

Analysis	Repeat stratified by ?	Repeat by Core Treatment Period?
Overall summary of AE	Yes	Yes
AEs by SOC/PT by descending frequency	Yes	Yes
AEs with an incidence of 5% or more by PT	Yes	Yes
Severe AEs by SOC/PT	Yes	Yes
AEs by maximum severity by SOC/PT	Yes	Yes
Related AEs by SOC/PT	Yes	Yes
SAEs by SOC/PT	Yes	Yes

Study: 221AD304 **Version:** 2.0

Analysis	Repeat stratified by ?	Repeat by Core Treatment Period?
Related SAE by SOC/PT	Yes	Yes
AEs led to discontinuation of study treatment by SOC/PT	Yes	Yes
AEs led to withdraw from study by SOC/PT	Yes	Yes
AEs led to drug interrupted, drug withdrawn by SOC/PT	Yes	Yes
SAEs with fatal outcome by SOC/PT	Yes	Yes
ARIA events led to treatment discontinuation	No	No

The following listings will be provided:

- (a) Listing of AEs
- (b) Listing of SAEs
- (c) Listing of AEs that led to discontinuation of study treatment
- (d) Listing of AEs that led to withdrawal from study
- (g) Listing of Deaths
- (h) Listing of non-treatment emergent AEs
- (i) Listing of AEs for participants with treatment-emergent anti-aducanumab antibody positive response

The listing of AEs contains the following information: participant number, investigator term, PT with reference ID, onset date, onset study day, end date, end study day, duration of AE (in days), outcome, severity, relation (related to study drug as assessed by the investigator), symptom of ARIA (yes/no), serious (yes/no), study withdrawal (yes/no), concomitant treatment (yes/no), and action on study treatment.

Study: 221AD304 Version: 2.0

5.7.3. AE of Special Interest 5.7.3.1. Background

ARIA-E and ARIA-H are considered AEs of special interest in this study. Protocol section 7.2.1 describes ARIA management and dose disposition guidelines. Since ARIA is a brain MRI finding, ARIA data are collected under two data sources: (1) safety MRI data as recorded on brain MRI worksheet by central MRI reader; (2) AE eCRF. For each ARIA event, the information of start/end date, severity, locations in brain regions and status on MRI scan is collected on the brain MRI worksheet by central MRI reader. ARIA severity is determined by the central MRI reader based on number and size of the ARIA regions on imaging. An AE record is then entered into the eCRF by the investigator with the start/end date and severity information from brain MRI worksheet, and with information on the symptomatic status and action taken towards study drug. If ARIA is symptomatic, the symptoms will be entered into AE eCRF and the severity of the symptoms will be determined by the investigator. AE eCRF data will be used as the primary source for ARIA analysis as it contains the complete information of ARIA as well as associated symptoms. Safety MRI data will also be used to show the consistency between two data sources, provide details on MRI assessments, and for any specific analysis that requires information from MRI.

ARIA includes ARIA-E (vasogenic edema) and ARIA-H (hemorrhage). ARIA-H includes ARIA-H microhemorrhage, ARIA-H macrohemorrhage and ARIA-H superficial siderosis. Table 5 shows the reported term on MRI worksheet, the corresponding reported term on AE eCRF, and the MedDRA preferred term for each type of ARIA.

Table 5 Verbatim Terms and MedDRA terms for ARIA

AESI	Verbatim term	MedDRA preferred term
ARIA-E	Asymptomatic ARIA-E or	Amyloid related imaging
	Symptomatic ARIA-E	abnormality-oedema/effusion
ARIA-H	Asymptomatic ARIA-H	Amyloid related imaging
microhemorrhage	(Microhemorrhage) or	abnormality-microhaemorrhages and
	Symptomatic ARIA-H	haemosiderin deposits
	(Microhemorrhage)	
ARIA-H superficial	Asymptomatic ARIA-H	Superficial siderosis of the central
siderosis	(Superficial Siderosis) or	nervous system
	Symptomatic ARIA-H	
	(Superficial Siderosis)	
ARIA-H	Asymptomatic ARIA-H	ARIA-H macrohemorrhages could be
macrohemorrhage	(Macrohemorrhage) or	coded to various preferred terms,
	Symptomatic ARIA-H	depending on type of hemorrhage and
	(Macrohemorrhage)	location of hemorrhage.
		Example: cerebral haemorrhage

Study: 221AD304 Version: 2.0

Events of ARIA-H macrohemorrhage have been added to the analysis of ARIA events based on historical considerations for the aducanumab program. These AEs were reported by Investigators based on designation of "macrohemorrhage > 1 cm diameter" by central MRI readers on the brain MRI worksheet. Because of the limitations of the MedDRA coding for such events (there is no MedDRA PT that is consistently used for ARIA-H macrohemorrhage), the event reporting included additional free text to describe other pertinent details of the event, such as the hemorrhage location.

For any specific ARIA event, the start date of the duration is the date of the MRI assessment that initially identifies the ARIA event, and the end date of the duration is the date of the MRI assessment that shows the complete resolution of this ARIA event (in the case of ARIA-E), or the date of the MRI assessment that shows ARIA being stable (in the case of ARIA-H). Stable is defined as 'No change' or a decrease in number, size, severity, or number of locations between 2 consecutive MRIs including the initial detection MRI and the follow-up MRIs performed 4 weeks (±5 days) later.

If the severity increases, or the event changes from asymptomatic to symptomatic, or from non-serious to serious, more AE records will be added to eCRF to capture the change with new start/end AE dates (the end date of the previous record will be the start date of the next record). For analysis, records with changes in severity or symptomatic status or seriousness are considered as a single ARIA event. The severity/symptomatic status/seriousness for that event is defined as the worst level among all the AE records that belong to that event.

If the same type of ARIA event happens again after the previous event has ended and both events occurred within the 221AD304 study, then it is considered a recurrent event of ARIA of that type. Recurrent events will be referred as the second event, the third event, etc.

If the duration based on MRI of an ARIA-E event overlaps with the duration based on MRI of an ARIA-H event, then these 2 ARIA events are considered as concurrent events.

All planned analyses described below are listed in Table 6. All analyses will be presented by safety analysis groups for the overall study. Where indicated, the analyses will be repeated by safety analysis groups stratified by

5.7.3.2. Incidence and summary of ARIA

Incidence of ARIA-E, ARIA-H, ARIA-E and ARIA-H (not necessarily concurrent), concurrent ARIA-E and ARIA-H, ARIA-E or ARIA-H, isolated ARIA-H (only ARIA-H, no ARIA-E), ARIA-H microhemorrhage, ARIA-H macrohemorrhage and ARIA-H superficial siderosis will be summarized based on both AE eCRF and MRI data, which will be stratified by ARIA-E status (No ARIA-E vs Had ARIA-E) in the feeder study when applicable. If there is any discrepancy in incidence between the two data sources, a listing of the subjects and ARIA events with discrepancy will be provided.

Number of subjects with each type of ARIA, maximum severity and worst symptomatic status of the type of ARIA will be summarized based on AE eCRF by safety analysis groups and safety analysis groups stratified by

Study: 221AD304 **Version:** 2.0

symptomatic status of each type of ARIA will also be summarized by safety analysis groups among subjects with ARIA in the study.

Onset of ARIA events will be summarized to present number of first and total ARIA and ARIA-E events, number of first and total symptomatic ARIA and ARIA-E events, and number of first and total serious ARIA and ARIA-E events.

ARIA-E resolution and ARIA-H stabilization will be summarized, and the following information will be presented: number of subjects with ARIA-E and ARIA-H, total number of ARIA-E and ARIA-H events, number of ARIA-E and ARIA-H events resolved and not resolved while on study, and MRI duration of the resolved ARIA-E and ARIA-H events. The MRI duration will be summarized as categorical variable (categories of 0-4, 0-8, 0-12, 0-16, 0-20, and >20 weeks).

An incidence table of AEs considered by the investigator to be related to ARIA by system organ class and preferred term will be provided, as well as a listing of these AEs.

Symptomatic ARIA will also be summarized. Number of subjects with symptomatic ARIA, number of symptomatic ARIA events, and MRI severity and symptomatic severity will be presented.

Number of subjects with serious or severe ARIA, or serious or severe ARIA symptoms will be summarized. Serious or severe ARIA-related AEs will be summarized by preferred term.

Summary of first ARIA-E events table based on AE eCRF will summarize the number of subjects with a first event of ARIA-E, the MRI severity of the events, the symptomatic status of the events, the severity of the symptoms for symptomatic events, whether the event is an SAE, number of resolved and unresolved events, duration of the resolved events, time from first infusion in study to onset, number of doses received since the start of the study to onset, dose level of the last infusion received prior to onset, dosing status (continue as planned, dose interrupted, dose reduced, or dose discontinued) after the events, and the number of subjects with recurrent ARIA-E events.

Summary of recurrent ARIA-E events based on AE eCRF will present the following information: number of ARIA-E event per subject, number of cumulatively ARIA-E events per subject, number of subjects with a first ARIA-E event and at least 1 dose and MRI after resolution of the first ARIA-E event, number of subjects experienced recurrent ARIA-E.

A listing of subjects who withdrew from the study with unresolved ARIA-E will be provided with the details of the event including the duration from onset to last follow-up.

A summary of ARIA-H will be provided for participants with or without ARIA-E in the study.

MRI assessments for subjects with ARIA-E, ARIA-H microhemorrhage, ARIA-H superficial siderosis, ARIA-H macrohemorrhage, other MRI abnormalities at postbaseline, and other ischemic abnormalities at postbaseline will be listed. The last dose level received before the MRI scan will be provided in those listings.

Study: 221AD304 **Version: 2.0**

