2.3. Study Conduct Following Announcement of Study Termination

On 19 September 2023, Biogen announced the decision to initiate early termination of the EMBARK study. At that time, all subjects had completed the core treatment period, and over 600 subjects were in LTE treatment period.

The requirement for scheduling the last dose visit and last safety follow-up visit was later updated as described in Table 1. Non-France participants were required to have the last-dose

Study: 221AD304 Version: 2.0

visit prior to 31 October 2023, and the safety follow-up visit 18 weeks after their last dose (+/-5 days) and no later than March 8th, 2024.

As there was no available post-trial compassionate access mechanism in France, French participants were allowed to remain on treatment as planned and complete the EMBARK LTE in full. As a result, the decision for early termination of the EMBARK study did not impact French participants in the study.

Following Biogen's announcement of termination of the aducanumab program, EMBARK study termination activities were initiated in France on 31 January 2024. Participants from France were required to have the last-dose visit prior to 01 May 2024, and the safety follow-up visit 12 weeks after their last dose (+/-5 days) and no later than 24 July 2024.

Table 1 Summary of Updates on Last Dose Visit and Safety Follow-up Visit since the Announcement of Study Termination

	Global ex	cluding France		France
Date of study				
updates	Last dose visit	Follow-up visit	Last dose visit	Follow-up visit
	Prior to	18 weeks after the	Prior to	18 weeks after the last
19Sep2023	19Oct2023	last dose	19Oct2023	dose
			Study continues	
	Prior to	18 weeks after the	as originally	
28Sep2023	31Oct2023	last dose	planned	
				30 days after last dose
		No later than	No later than	and no later than
31Jan2023		31Mar2024	01May2024	01Jun2024
		18 weeks after their		12 weeks (90 days)
		last dose (+/-5 days)		after their last dose (+/-
		and no later than		5 days) and no later
22Feb2024		08Mar2024		than 24Jul2024

Changes to Study Execution Following Announcement of Study Termination

The changes to study execution in France sites involve the following, as described in 221AD304 Protocol Clarification Letter 13Feb2024.

1. End of Treatment (EoT) visit (Section 4.2, Table 3)

In Version 4 of the protocol, Section 4.2 Schedul-	e of Events Table 3 currently includes
timepoints for the	as well as clinical efficacy and
safety assessments.	

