Study: 221AD304 Version: 2.0

Clarification Statement

Due to the discontinuation of the Aducanumab program and the early termination of the study,

[figure not shown]
Also, to reduce participant burden, the clinical efficacy assessments will be removed, leaving only safety assessments.

2. Follow-up/End of Study (FU/EOS) Visit: assessments and timing (Section 4.2, Table 3)

Version 4 of the current protocol mandates that participants return for a Follow-up/End of Study visit (also referred to as the safety follow-up visit) 18 weeks after the participant's last dose at 152 weeks (see Section 4.2, Table 3, Schedule of Activities).

Clarification Statement

Due to the discontinuation of the Aducanumab program and the early termination of the study, all participants will be asked to complete their Follow-up/End of Study Visit 12 weeks (+/– 5 days) after the participant's last dose of study treatment. In addition, similar to the End of Treatment Visit, the number of assessments that need to be completed is now reduced to lessen participant burden. These assessments are reported below in Table 2. If a participant has had their last dose of study treatment and it has been more than 12 weeks since their last dose and the participant has not had their safety follow-up, then they should complete a safety follow-up within the next 30 days, as defined in Table 2.

Study: 221AD304 Version: 2.0

Table 2 Revised Schedule of Assessments for the End of Treatment and Follow-up Visits

Study Assessments	Week 154/End of Treatment Visit (within 2 weeks of last dose)	Follow up/End of Study Visit (12 weeks after last dose +/- 5 days)
Body Weight	X	
Hematology, Blood Chemistry, and Urinalysis	X	
Alzheimer's Disease Status	No longer being completed	
Physical Examination	X	X
Neurological Examination	X	X
Vital Signs	X	X
12-Lead Paper ECG	X	
ADA	X	
Aducanumab Serum Concentration	X	

Study: 221AD304 Version: 2.0

Study Assessments	Week 154/End of Treatment Visit (within 2 weeks of last dose)	Follow up/End of Study Visit (12 weeks after last dose +/- 5 days)	
C-SSRS	X	X This will now be completed	
Brain MRI		X	
AE Reporting	Monitor and record continuously throughout the study		
Concomitant Therapy and Procedures	Monitor and record continuously throughout the study		
SAE Reporting	Monitor and record continuously throughout the study		

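### The ARIA resolution tables pool events never re-imaged with events shown to persist, and during the LTE the only routine MRI is at the final follow-up visit

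*SAP*

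**What the plan says.** **Outcome classes.** The resolution and stabilization table in SAP 5.7.3.2 gives the "number of ARIA-E and ARIA-H events resolved and not resolved while on study". The first ARIA-E table in the same section has the same two classes: "number of resolved and unresolved events, duration of the resolved events".

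**What closes an event.** SAP 5.7.3.1 ends an ARIA-E event on "the date of the MRI assessment that shows the complete resolution of this ARIA event (in the case of ARIA-E"). It ends an ARIA-H event once stability is shown "between 2 consecutive MRIs including the initial detection MRI and the follow-up MRIs performed 4 weeks (±5 days) later".

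**When routine scans occur.** Protocol Table 4 schedules brain MRI at Screening, at Weeks 14, 22, 30, 42, 54, 66, 78 and 102, and then only at the LTE follow-up visit (Week 170, or 18 weeks after the last dose). SAP Table 2, the revised schedule for France, also marks MRI only at the follow-up/EOS visit and not at Week 154.

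**Dates after termination.** SAP 2.3 requires, outside France, "the safety follow-up visit 18 weeks after their last dose (+/-5 days) and no later than March 8th, 2024". In France the visit is 12 weeks after the last dose and no later than 24 July 2024.

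**Listing of unresolved cases.** "A listing of subjects who withdrew from the study with unresolved ARIA-E will be provided", with duration from onset to last follow-up. It covers ARIA-E only.

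**The concern.** An event can be unresolved for two different reasons: a later MRI showed it persisting, or no later MRI was done. The planned tables give one count for both. The distinction matters most for ARIA first seen on a participant's last scheduled scan, because that scan cannot itself show resolution or stability. In the LTE the last scheduled scan is also the only routine one, so ARIA without symptoms that arose after Week 102 would usually come to light there.

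At stake is the reading of the overall-study resolution table, which tells a safety reader whether ARIA clears or stabilizes under long-term treatment. A raised unresolved count could be taken for longer-lasting ARIA when it reflects the end of imaging. No other planned summary separates the two groups: SAP section 7 removes the time-to-event analyses, and MRI duration is tabulated for resolved events only.

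**Working it through.** **1. Reproduce the plan's MRI count.** Protocol 7.3 states 10 MRI visits. Counting the scheduled marks in Protocol Table 4, without the unscheduled ARIA column, gives 9 through Week 102 plus 1 afterwards = 10. The figure reproduces.

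**2. Gap before the last scan.** Week 102 is Day 714 and Week 170 is Day 1190. 1190 − 714 = 476 days, and 476 / 7 = 68 weeks without a routine MRI on the full schedule.

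**3. Where a confirmatory scan would fall.** Four weeks ± 5 days is 23 to 33 days after detection.
- Outside France, visit on the limit of 8 March 2024: scan due 31 March to 10 April 2024.
- France, visit on the limit of 24 July 2024: scan due 16 to 26 August 2024.
- A 28-day scan fits before the limit outside France only if the visit was by 9 February 2024, which means a last dose by about 6 October 2023 (126 days earlier).
- In France the visit must be by 26 June 2024, which means a last dose by about 3 April 2024 (84 days earlier).

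These limits apply to the follow-up visit. Nothing in the documents bars a later unscheduled MRI.

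**4. Does the follow-up rule reach the last visit?**
- Protocol 7.2.1.1 to 7.2.1.4 call for unscheduled MRIs until ARIA-E resolves or ARIA-H is stable. For micro-hemorrhage and superficial siderosis they refer to events at any time in the study.
- Protocol 7.3 directs participants with ARIA in the Treatment Period to those visits and is silent on ARIA first found at follow-up.
- Protocol 15.3.1 has adverse events ongoing at study completion followed until resolved, stabilized or back to baseline.
- SAP 3.1 takes the EOS date from the eCRF page, while SAP 3.3 runs the LTE period to the last assessment in any database. SAP 5.7.3.2 does not say which of the two defines on study.

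So a later scan may well exist, but the plan does not settle whether it counts.

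**5. Illustration of size (assumed inputs).** Let E be the events with a later MRI, of which 98.2% resolve. That rate is borrowed from the 800 of 815 participants with a resolved first ARIA-E in Protocol 5.4. Let k = 600 × p be events first seen on the final scan and never re-imaged; SAP 2.3 gives over 600 participants in the LTE. E and p are assumptions.

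Reported percentage resolved = 0.982 × E / (E + k)

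| E | p = 1% (k = 6) | p = 3% (k = 18) | p = 5% (k = 30) |
|---|---|---|---|
| 200 | 95.3% | 90.1% | 85.4% |
| 400 | 96.7% | 94.0% | 91.3% |

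For example, 0.982 × 200 / 230 = 196.4 / 230 = 85.4%. Among events with a later MRI the figure stays at 98.2% in every cell.

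**The case against.** A reader might infer that ARIA found on the final scan is counted as unresolved by design. The documents do not support that. The protocol asks for re-imaging until resolution or stability and for continued follow-up of ongoing adverse events, and SAP 3.3 lets a later assessment fall inside the LTE period. Such an event is unresolved only if no later MRI was done and entered, or if the analysis ignores it. Nor can one infer that completers with unresolved ARIA-E disappear from the report. The MRI listings in SAP 5.7.3.2 and the adverse event listing in SAP 5.7.2.2 are not limited to withdrawals, so the facts can be reconstructed by hand.

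Two further arguments have weight. Counting an event without a later scan as not resolved while on study is literally true and conservative for safety, and removing such events from the denominator would raise the reported resolution. The stakes are also limited: the core primary ARIA endpoint is incidence, and SAP 5.1 plans no testing.

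These points reduce the size of the problem and argue against a single restricted denominator. They do not remove the pooling. Wherever no later MRI exists, for whatever reason, the tables cannot show it.

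**Conclusion.** The point holds in a limited form. SAP 5.7.3.2 does not distinguish persistence on re-imaging from absence of re-imaging, and it leaves open how an MRI after the EOS visit is treated. This can inflate the not-resolved count in the overall-study tables. The core-period repeat has a smaller version of the same gap, because participants who do not enter the LTE have no routine MRI after Week 102; they do remain under observation to Week 118.

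The size is unknown. The range of 85.4% to 96.7% against 98.2% rests on assumed event counts, on no re-imaging of the late events, and on a resolution rate for first ARIA-E that need not apply to ARIA-H. It shows direction and plausible scale and is not an estimate.

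The SAP already makes this kind of distinction elsewhere. Its seizure summary (5.7.4) has a non-evaluable ARIA class for subjects without a post-baseline MRI. This is a cheap improvement and does not affect the incidence results.

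**What to change.** 1. In the resolution and stabilization table and in the first ARIA-E table, divide the unresolved class into *not resolved on at least one later MRI* and *no MRI after detection*, using existing MRI dates.
2. Report the percentage resolved (or stable) both among all events and among events with a later MRI, so that neither choice of denominator hides the other.
3. State in SAP 5.7.3.2 that any MRI in the database after the EOS visit counts towards resolution or stability.
4. Extend the unresolved ARIA-E listing from subjects who withdrew to all subjects with ARIA-E unresolved at their last MRI.
5. Reconcile Protocol 7.3 with Protocol 7.2.1 on whether the unscheduled visits cover ARIA first found at follow-up, or record in the SAP how this was applied.

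Optionally, the dosing-status rows of the first ARIA-E table could label events found after the final dose, since the four planned categories do not describe them.

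The cost is one derived flag, a few table rows and a few lines of SAP text. No new data are needed.
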